A Preliminary Study of Prophylactic Fentanyl Sublingual Spray (FSS) for Exercise-Induced Breakthrough Dyspnea

Principal investigator: [name]

Supportive Care Co-investigator: [name]

Collaborators: [name], [name]

Table of Contents

A. Study Objectives	2
B. Background.....	2
C. Experimental Approach	2
D. Statistical Analysis	12
E. Data Confidentiality Procedures.....	13
F. References.....	14

A. Study Objectives

Primary objective:

To determine the **effect of prophylactic fentanyl sublingual spray** (FSS, 15-25% and 35-45% proportional doses) on the **intensity of exercise-induced dyspnea** (modified Borg scale) between the first and second shuttle walk tests. *We aim to estimate the effect size for both FSS arms to inform a larger, adequately powered confirmatory randomized controlled trial.*

Secondary objectives

A.2. To determine the **effect of prophylactic FSS** (15-25% and 35-45% proportional doses) on **walk distance and adverse effects** between the first and second shuttle walk tests. *We hypothesize that FSS is superior to no FSS in increasing walk distance and has limited side effects in opioid tolerant individuals.*

A.3. To compare the **intensity of exercise-induced breakthrough dyspnea** between high (35-45% proportional dose) and low (15-25% proportional dose) doses of prophylactic FSS. *We hypothesize that higher doses of FSS is superior to lower doses FSS in reducing dyspnea at the end of the shuttle walk test.*

B. Background

Dyspnea is a subjective awareness of difficulty breathing, which may be associated with the distressing sensation of suffocation. It is one of the most common and most feared symptoms among cancer patients, occurring in up to 70% of patients in the last 6 weeks of life ^{1,2}. Dyspnea is associated with fatigue, anxiety, decreased function and quality of life, and increased mortality ^{3,4}.

In a study examining 70 patients with dyspnea, 43 (61%) reported breakthrough (episodic or incidental) dyspnea only, 13 (19%) had constant dyspnea only, and 14 (20%) experienced both constant and breakthrough dyspnea. A substantial proportion of the patients with breakthrough dyspnea (18/57, 32%) presented with 5 or more episodes per day, and the majority of episodes lasted <10 minutes ⁵. Breakthrough dyspnea is particularly challenging to treat because of its transient and episodic nature.

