not take the study medication is as follows: In CTC, edit the patient to be replaced modifying MRN within the specific patient's stratum. Then add a history of the changes made to the Notes section. Randomization will be 1:1 between the two study arms with permuted blocks, and stratified by baseline level of dyspnea modified Borg scale at rest at the time of enrollment (i.e. 0-3, 4-6).

C.5. Blinding. Both the patient and the research staff conducting the assessment will be blinded to the treatment assignment. FSS will be dispensed by Dispensing Pharmacy at MD Anderson. Only research nurse administering the medication will be aware of the study dose, and will be instructed not to share that information with the patient and other research staff. Further to that, we will check the blinding from patients and study staff at the end of study.

C.6. Research staff. An orientation will be held with research staff involved in this study to introduce them with the study design and to standardize the provision of each intervention.

C.7. Study Interventions. The commercial supply of study medication will be provided by Insys Therapeutics Ltd. We will use a one time prophylactic FSS dose equivalent to either 15-25% or 35-45% of MEDD 10 minutes prior to the second shuttle walk test. FSS was FDA approved in 2012 for "For the management of breakthrough pain in adult cancer patients who are already receiving and who are tolerant to around-the-clock opioid therapy for their underlying persistent cancer pain."

Immediately upon patient enrollment, the study physician will be notified and will determine the morphine equivalent daily dose (MEDD) in real time using standardized equianalgesic ratios. Based on clinical practice and similarly to the dose used for breakthrough pain, we will use an FSS dose equivalent to 15-25% or 35-45% of MEDD (Table 3). The study medication will be provided by Dispensing Pharmacy and will then be administered 10 minutes before the second shuttle walk test. We estimated the FSS dose based on the following assumptions:

- A one time rescue dose 15-45% of the MEDD is safe and effective for relief of dyspnea
- FSS has approximately 70% oral bioavailability ³⁰

Table 3. Proportional Dosing of FSS for patients randomized to the two study arms

High dose (target 35-45% MEDD)				Low dose (target 15-25% MEDD)			
MEDD (mg/day)	FSS dose*	% of MEDD - low	% of MEDD - high	MEDD (mg/day)	FSS dose*	% of MEDD - low	% of MEDD - high

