Dyspnea Numeric Rating Scale ⁷	✓	✓		✓	✓
Walking test parameters ⁹		✓			✓
Adverse effects ¹⁰				✓	✓
Neurocognitive testing ¹¹		✓			✓
Global assessment, study satisfaction and blinding ¹²					✓

¹ patient initials, medical record number, date of birth, sex, race, education, marital status, cancer diagnosis, co-morbidities, cause(s) of dyspnea, bedside spirometry and maximal inspiratory pressure.

² medications that could be used to treat dyspnea, including scheduled and as needed opioids, bronchodilators, and steroids will be documented.

³ an 11-point assessment scale that rates patients' functional status between 0% (death) and 100% (completely asymptomatic) based on their ambulation, activity level, and disease severity ³⁷.

⁴ validated questionnaire that measures 10 common symptoms in the past 4 hours (pain, fatigue, nausea, depression, anxiety, drowsiness, shortness of breath, appetite, sleep, and feeling of well being) using numeric rating scales ³⁸.

⁵ characterization of patients dyspnea including the following: presence of dyspnea at rest, average dyspnea in last 24 hours, worse dyspnea in last 24 hours, best dyspnea in last 24 hours, number of episodes of exacerbation per day, triggers of breakthrough dyspnea, average duration of each episode, current treatment for breakthrough dyspnea.

⁶ validated 12-item questionnaire specifically designed to assess the quality of dyspnea in

cancer patients during the past few days ³⁹. Each item has a score between 1 and 5, for a maximum of 60. There are sub-scores for sense of effort, anxiety, and discomfort.

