⁷ a 0 to 10 categorical scale for rating the severity of dyspnea. It is a ratio scale with descriptive anchors throughout the range in which a rating of 8 signifies breathlessness twice as severe as 4, which in turn is twice as severe as 2 ⁴⁰⁻⁴³. We will be measuring it every minute during the shuttle walk test starting from 0 minutes until the end of walk. This will be the primary endpoint because it has good reliability and validity for assessing dyspnea ^{40,41,44} and has been used in multiple other studies on exertional dyspnea ⁴⁵⁻⁴⁸. The minimal clinically important difference is 1.0 in patients with chronic obstructive pulmonary disease ⁴⁹. This scale can be administered quickly, and was found to be easy to use by patients ⁴¹. In a study that compared the dyspnea modified Borg Scale, numeric rating scale and visual analog scale, the modified Borg scale was preferred by participants and was recommended as the best tool to quantify dyspnea intensity ⁵⁰. Furthermore, its use is recommended by the American Thoracic Society and American College of Chest Physicians for Cardiopulmonary Exercise Testing ⁵¹.

⁸ a 0 (no dyspnea) to 10 (worst dyspnea) categorical scale validated for rating the severity of dyspnea ^{40,42,43}. The intensity and unpleasantness of dyspnea will be measured using the Borg scale 10 minutes prior to the shuttle walk test, every minute during the shuttle walk test until the end of the walk, and immediately after each shuttle walk test

⁹ include the total distance walked, total walking time, the distance and time of first rest due to dyspnea, average walking speed.

¹⁰ adverse effects related to the use of FSS, such as dizziness, drowsiness and nausea will be assessed using a numeric rating scale from 0-10.

¹¹ patients will be asked to do a finger tapping test, simple math test, reverse memory of digits, and visual memory). This has been used in other studies by our group. ⁵²

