Insys will be responsible for payment of the actual and reasonable medical expenses incurred in diagnosing and treating any injury, illness or adverse reaction of a study subject that results from the administration of Fentanyl Sublingual Spray.

C.15 Serious Adverse Event Reporting (SAE) Reporting

Serious adverse events will be captured from the time of the first protocol-specific intervention, until 14 days after the last dose of drug, unless the participant withdraws consent. Serious adverse events must be followed until clinical recovery is complete and laboratory tests have returned to baseline, progression of the event has stabilized, or there has been acceptable resolution of the event.

D. Statistical Analysis

D.1. Power Calculation. This pilot study is based on a sample of 15 evaluable subjects per arm, for a total of 30 patients. We expect to enroll approximately 2-3 patients per month for this study. Thus, we expect to complete the study in approximately 10-12 months.

The primary objective of determining effect size for powering future studies is collecting data on the distributional properties of dyspnea scores for the two arms. This study is not powered to test differential treatment effects between the two treatment groups measured by dyspnea modified Borg scores. Instead, with 15 patients in each group, we will have an 80% power to detect an effect size of 0.778 in difference of the dyspnea modified Borg score change after a shuttle walk test before and after the treatment (i.e., between the first and second shuttle walk) using a two-sided paired t-test with a significance level of 0.05.

D.2. Data Analysis. Summary descriptive statistics will be provided for demographics, outcomes, and other collected variables such as the change of exercise induced dyspnea, walk distance, neurocognitive function and various physiological parameters at the end of each walk and the difference of these changes between two walks, and will include proportions, medians, means, 95% confidence intervals, and other simple statistics as appropriate for the measure. Each endpoint will be evaluated repeatedly

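### Objective A.2 asks for the change in adverse effects from walk 1 to walk 2, but the 0-10 adverse-effect rating is not scheduled at walk 1

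*Combined protocol and SAP*

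**What the plan says.** Objective A.2 (section A) names two outcomes, "walk distance and adverse effects", and asks for the effect of FSS on both from walk 1 to walk 2. Its hypothesis reads: "We hypothesize that FSS is superior to no FSS in increasing walk distance and has limited side effects in opioid tolerant individuals".

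Footnote 10 to Table 5 gives the instrument: "adverse effects related to the use of FSS, such as dizziness, drowsiness and nausea will be assessed using a numeric rating scale from 0-10". It gives no time of assessment. In Table 5 (C.12) the row "Adverse effects ¹⁰" is ticked in two of the five time columns, before and after the 2nd walk. The row "Neurocognitive testing ¹¹" is ticked after the 1st and after the 2nd walk, as is the walking-parameters row.

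D.2 plans descriptive summaries of a list of outcomes introduced by 'such as'. The list includes "neurocognitive function and various physiological parameters at the end of each walk and the difference of these changes between two walks". Adverse effects are neither named in it nor excluded from it.

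**The concern.** The objective needs a value at each walk, and the schedule supplies one for walk 2 only. Walk 1 is the only exertion without FSS in this trial, because both arms are dosed and differ only in dose. C.9 says that walk 1 is there partly so that each patient can be compared with himself or herself. Leaving the symptom rating out at that point removes the reference against which symptoms after walk 2 would be judged.

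The patients have active cancer and already take 80-500 mg MEDD of strong opioids. Drowsiness and nausea are among the symptoms that footnote 4 calls common. A raised score after walk 2 could therefore reflect the illness, the regular opioid, the exertion or the study dose. The comparison between doses is a weak substitute: there are 15 patients per arm, and D.1 says the study is not powered for differences between arms even on the Borg score.

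**Working it through.** **The plan's own figure.** The only power statement (D.1) is 80% power for an effect size of 0.778 with 15 patients, by a two-sided paired t-test at 0.05. With 14 degrees of freedom and noncentrality 0.778 × √15, the exact power is 0.79998, so the figure reproduces. It concerns the Borg change and is not affected by this point.

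**The schedule (Table 5).**

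| Row | Baseline | After 1st | Rest | Before 2nd | After 2nd |
|---|---|---|---|---|---|
| Walking parameters | | ✓ | | | ✓ |
| Neurocognitive testing | | ✓ | | | ✓ |
| Adverse effects, 0-10 | | | | ✓ | ✓ |
| Edmonton scale (ESAS) | ✓ | | | | |

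A change between walks needs a value in both the after-1st and the after-2nd columns. Walk distance has both. The adverse-effect rating has only the second. C.9 adds Borg ratings, vital signs, time, distance and the stated reason for stopping at each walk, but not this rating. Patients who can have the change on this scale: 0 of 30, or 0 of 15 per arm.

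**Can the rating before walk 2 serve instead?** Footnote 10 does not time it. Footnote 8 says that dyspnea "will be measured using the Borg scale 10 minutes prior to the shuttle walk test", and C.7 has the spray "administered 10 minutes before the second shuttle walk test"; C.10 agrees on the 10-minute wait. This suggests that the column falls at about the time of dosing, but not on which side of it. The clue is also weak because footnotes 7 and 8 appear to be swapped: footnote 7 is attached to the numeric rating scale but describes the Borg scale. There are two cases:

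- Before the spray: the rating is drug-free but taken after rest, once dyspnea and fatigue are back to within 1 point of baseline (C.10). The change from it to after walk 2 mixes drug with exertion.
- After the spray: no drug-free rating exists on this scale at all.

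Neither case gives a rating straight after exertion without FSS.

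**Can other data serve instead?** Only in part. ESAS covers nausea and drowsiness but not dizziness, has a 4-hour recall and is given once. Neurocognitive tests, vital signs and stopping reasons exist for both walks but are different measures.

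**What the added rating would give.** At most 15 pairs per arm. There could be fewer, because C.11 can stop patients after dosing and replaces only those lost before the drug. The number of added ratings is 3 symptoms × 30 patients = 90. This is close to a minimum: the symptom list in footnote 10 is open, and patients who are later replaced may also do walk 1.

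**The case against.** The best counter-argument is that this is a mismatch of wording. In the A.2 hypothesis, superiority over no FSS attaches to walk distance; the adverse-effect clause claims only that side effects are limited. Footnote 10 concerns effects related to FSS, and none has been given at walk 1. A.2 also speaks of adverse effects in general, and neurocognitive function and physiological measures, which D.2 does compare between walks, may be meant to cover part of it. Finally, the added contrast would itself be imperfect.

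Much of this stands as a limit on scope. Low scores after walk 2 would support the hypothesis without any walk-1 value. The neurocognitive and vital-sign changes can be estimated, although the protocol does not say that they serve A.2. The point therefore concerns the 0-10 scale only.

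It does not remove the gap. Dizziness, drowsiness and nausea are non-specific symptoms, and attributing them to FSS needs a value without FSS. The objective itself, as distinct from the hypothesis, asks for the effect between walks on both outcomes.

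The objection about imperfection is fair but applies equally to the dyspnea and distance contrasts, which the plan accepts.

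**Conclusion.** The point holds. On the 0-10 scale, the between-walk contrast named in A.2 cannot be computed for any of the 30 planned patients. What remains possible is a description after walk 2, a comparison between doses, and, if the rating before walk 2 precedes the spray, a change from rest before dosing to after walk 2.

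The conclusion rests on reading the Table 5 ticks against their column headings, and on there being no other section that schedules this rating at walk 1. It does not depend on the unresolved timing of the rating before walk 2; that timing decides only whether any drug-free rating exists.

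The consequence is modest: one secondary objective, one symptom scale, a descriptive pilot. It is still worth correcting before enrolment, because the visit is single and a rating not taken after walk 1 cannot be recovered.

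**What to change.** **Preferred.**

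- In Table 5, add the same 0-10 dizziness, drowsiness and nausea ratings after walk 1, alongside the neurocognitive tests.
- In footnote 10, state whether the rating before walk 2 is taken before or after the spray.
- In D.2, summarise the within-patient change (after walk 2 minus after walk 1) by arm with a 95% confidence interval and the number of complete pairs, next to the change in walk distance.
- State the limits. The change stays confounded with walk order, fatigue and walk length. The test is symptom-limited and A.2 expects a longer walk 2; by Table 4, completing level 5 rather than level 4 means 250 − 180 = 70 m and 60 s more walking. Dizziness will carry little information, because C.11 stops patients who develop it.

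The cost is about three short questions per patient, roughly 90 ratings in all or somewhat more if replaced patients also do walk 1. No extra visit or staff is needed.

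**If the rating is not added.** Reword the adverse-effect part of A.2 as a description after walk 2 and a comparison between doses, and still state the timing in footnote 10. This costs wording only, but A.2 would then no longer address a change in adverse effects between walks.

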80-100	200	35.0	43.2	80-130	100	13.5	21.6
101-150	300	35.0	52.0	131-210	200	16.7	26.7
151-200	400	35.0	46.4	211-280	300	18.8	24.9
201-250	500	35.0	43.5	281-450	400	15.6	24.9
251-300	600	35.0	41.8	451-500	600	21.0	23.3
301-400	800	35.0	46.5				

401-500 1000 35.0 43.6 |

* FSS comes in 100 mcg, 200 mcg, 400 mcg, 600 mcg and 800 mcg. A combination of these products would allow us to deliver the desired dose.

The following instructions will be given to the patient:

1. Swallow any saliva in your mouth.
2. Hold the medication spray unit upright using your index and middle fingers and thumb.
3. Point the nozzle into your mouth and under your tongue.
4. Squeeze your fingers and thumb together to spray the medication under your tongue.
5. Hold the medicine under your tongue for 30-60 seconds. Do not spit out any medicine. Do not rinse your mouth.
6. The spray unit will remain locked after use.

C.8. Medication use during study. To minimize the co-intervention effect on dyspnea, patients will be advised to avoid using breakthrough opioids (for any reason) or bronchodilators for at least 2 hours prior to and during the study.

C.9. The Shuttle walk test is an externally paced test, and has been found to be high reproducible for inducing breathlessness in patients with advanced cancer ³¹⁻³³. Furthermore, the shuttle walk test was reported to be equivalent or better than 6 minute walk test in detecting a clinical response ³⁴⁻³⁶. Shuttle walk tests will be conducted according to published procedures ³¹⁻³³. The first shuttle walk test is designed to provide important information regarding a patient's level of dyspnea on exertion, and to facilitate intra-individual comparison since there is significant variability in the expression of dyspnea among patients. The second shuttle walk test will be conducted 10 minutes after study medication has been administered.

The research staff conducting the walk test must be certified in cardiopulmonary resuscitation with a minimum of Basic Life Support by an American Health Association-approved cardiopulmonary resuscitation course. Walking aid is allowed as long as patients keep them the same as before enrollment and during the entire study.

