We will be assessing the dyspnea level with modified Borg scale at baseline and then every minute during at the shuttle walk test as well as at the end. We will also measure the heart rate, respiratory rate, blood pressure, oxygen saturation before and immediate after the shuttle walk test. The total walking time and distance will also be measured. We will also ask the reasons for stopping or being unable to keep up with the required pace using a standardized statement and question: "You had to stop, what was it that made you stop the test?" The patients' comments were recorded verbatim.

C.10. Variable rest period. After the first and second shuttle walk test, patients will be asked to sit down and rest. How long they rest would depend on when they return to baseline level of dyspnea + 1 or below (e.g. if baseline dyspnea = 4, they need to return to a level of 5 or less to qualify for next stage) and baseline level of fatigue +1 or below. During this rest period, patients will be assessed every 5 minutes to check their dyspnea and fatigue level. If their dyspnea/fatigue level met criteria and they feel ready

to walk again, they will be given the study treatment and asked to wait for 10 minutes before they do the second walk.

C.11. Stopping rules. In the unexpected situation in which patients do not develop any increase from their baseline dyspnea after the first shuttle walk will not proceed to the next stage because of the lack of exercise-induced dyspnea. If at any time during the study patients develop chest pain, severe leg cramps, staggering, diaphoresis, and/or dizziness, they will be asked to stop the study. If patients require more than 1 hour of rest and their dyspnea and fatigue level still has not returned to baseline, they will also be taken off study. Patient dropouts and walk test failures prior to the administration of drug will be replaced.

C.12. Study assessments. See Table 5 for a detailed description of all study assessments.

Table 5. Summary of Study Assessments

Assessments	Baseline	After 1 st shuttle walk test	Rest Period	Before 2 nd shuttle walk test	After 2 nd shuttle walk test
Demographics and cancer diagnosis ¹	✓				
Medication history ²	✓				
Karnofsky performance status, spirometry testing, and inspiratory pressure ³	✓				
Edmonton Symptom Assessment Scale ⁴	✓				
Dyspnea Survey ⁵	✓				
Cancer Dyspnea Scale ⁶	✓				
O ₂ saturation and respiratory rate	✓	✓		✓	✓
Dyspnea Borg/fatigue scale ⁸	✓	✓	✓	✓	✓

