during the 1st and 2nd walk tests when appropriate. Repeated measures analysis may be employed to evaluate the change of these measures over time during each walk. We will also evaluate the effect of distance walked on the dyspnea in the repeated measures analysis, when possible. The effect of treatment on the changes of these measures will also be estimated in the same model when possible. Other statistical methods may be applied when appropriate.

E. Data Confidentiality Procedures

Health information will be protected and we will maintain the confidentiality of the data obtained from the patients' charts.

Collection of identifiers: We will collect and securely store patients' identifiers (including name, medical record number, and demographic specifications). Each patient will be assigned a study number that will be the only identifier to figure in the analytical file and personal data will not be disclosed in any form. The key linking these numbers will be retained in a securely locked file by the investigator.

Data Storage: Protection of electronic and paper records will be maintained to the best of our ability. All electronic records will be stored on password-protected institution computers behind the institution firewall. Any paper records will be classified and stored in locked files inside a locked office.

Training of personnel: Only MDACC personnel trained in maintaining confidentiality, the principal investigator, co-investigators, collaborators, and research staff will have access to study records.

Data sharing: Study data will not be shared with any individuals or entities without prior IRB-approval. The data will be kept by the principal investigator in a locked file cabinet or password-protected computer.

Final disposition of study records: Once the research has been completed, identifiers will be retained for as long as is required by law and by institutional regulations, and at that point will be destroyed. PHI may be maintained indefinitely, aggregated in the future, and used for future research studies.

F. References

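### D.2 assigns no explicit analysis to the high-versus-low dose contrast (A.3); naming an ANCOVA on Walk 1 dyspnea and the stratum would be a cheap, usually modest gain in precision

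*Combined protocol and SAP*

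**What the plan says.** Section A.3 sets the between-dose hypothesis: "We hypothesize that higher doses of FSS is superior to lower doses FSS in reducing dyspnea at the end of the shuttle walk test". Section C.4 randomises 1:1 "with permuted blocks, and stratified by baseline level of dyspnea modified Borg scale at rest at the time of enrollment (i.e. 0-3, 4-6"). Section C.9 explains that the first walk is there "to facilitate intra-individual comparison since there is significant variability in the expression of dyspnea among patients".

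Section D.2 promises descriptive summaries for each walk and for the difference between walks. It then allows a repeated-measures analysis of change over time during each walk, in which the effect of distance walked will also be examined. On treatment it says only: "The effect of treatment on the changes of these measures will also be estimated in the same model when possible". It closes by permitting other methods. It does not cite A.3 or mention high versus low dose. No section names Walk 1 dyspnea or the stratum as a covariate.

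Section D.1 states that the study is not powered for the comparison between arms. Its power statement (80%, effect size 0.778, n = 15) concerns the paired comparison within an arm.

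**The concern.** The design collects a strong baseline (dyspnea at the end of Walk 1) and balances the arms on resting dyspnea, but the analysis text uses Walk 1 only as part of a change or as a repeated outcome, and does not use the stratum. In a randomised comparison, a contrast of changes fixes the Walk 1 coefficient at 1, while ANCOVA estimates it and is generally at least as precise, apart from a small price for the estimated terms.

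The study exists to supply effect sizes and distributional data for a confirmatory trial. As D.2 stands, the A.3 estimate and the residual SD passed on to that trial depend on a model chosen later.

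A related point concerns distance. D.2 places the treatment effect in the same model that examines distance walked. Section C.9 says "The total walking time and distance will also be measured" and also "The second shuttle walk test will be conducted 10 minutes after study medication has been administered", so total Walk 2 distance is a post-dose outcome. A.2 expects the drug to change it: "We hypothesize that FSS is superior to no FSS in increasing walk distance". Adjusting the A.3 estimate for it would change what is being estimated.

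**Working it through.** **Inputs from the documents.** 15 evaluable patients per arm, N = 30 (D.1); 1:1 allocation with two strata (C.4); minimal clinically important difference (MCID) of 1.0 on the Borg scale (C.12, Table 5 footnote 7).

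**Assumed, because the documents do not give them.** The correlation rho between end-of-Walk-1 and end-of-Walk-2 Borg; k = Walk 2 SD / Walk 1 SD; the SD itself; for the simulation, block size and the split between strata.

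**1. The plan's own figure.** A paired t-test with n = 15, two-sided 0.05 and the exact noncentral t has power 0.79998 at an effect size of 0.778. The figure reproduces and is not in question.

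**2. Variance of the two contrasts.** With Walk 1 SD = 1 and Walk 2 SD = k:

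- Change (end of Walk 2 minus end of Walk 1): proportional to 1 + k² − 2k·rho.
- ANCOVA: proportional to k²(1 − rho²), times an inflation for the estimated covariates. This is 1 + 1/26 = 1.038 for Walk 1 alone, and 1 + 2/25 = 1.080 for Walk 1 plus an unbalanced, uninformative stratum.
- Before inflation the difference is (1 + k² − 2k·rho) − k²(1 − rho²) = (1 − k·rho)² ≥ 0. ANCOVA can therefore lose only through the inflation, and most when k·rho = 1.

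Example, k = 1 and rho = 0.7: change 2 − 1.4 = 0.60; ANCOVA 1 − 0.49 = 0.51; ratio 0.85; with inflation 0.85 × 1.038 = 0.88 to 0.85 × 1.080 = 0.92.

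Ratio ANCOVA/change (Walk 1 only, then Walk 1 plus uninformative unbalanced stratum):

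| k | rho 0.5 | rho 0.7 | rho 0.9 |
|---|---|---|---|
| 0.9 | 0.69-0.72 | 0.78-0.81 | 0.84-0.88 |
| 1.0 | 0.78-0.81 | 0.88-0.92 | 0.99-1.03 |
| 1.1 | 0.85-0.88 | 0.96-1.00 | 1.04-1.08 |
| 1.25 | 0.93-0.96 | 1.02-1.06 | 0.99-1.03 |

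**3. Simulation with stratified blocks.** 15,000 trials per scenario, normal scores, 30% in the upper stratum, blocks of four, resting/walk correlation 0 or 0.5. Adjusting for Walk 1 and stratum gave ratios at k = 1 of 0.73-0.77, 0.86-0.88 and 0.99 for rho 0.5, 0.7 and 0.9. The largest cost in any scenario was 4%. Coverage of the change-score interval was 0.946-0.953 throughout.

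**4. What this means on the Borg scale.** Half-width of the 95% CI with equal SDs: change, t(28)·SD·√(2(1 − rho))·√(2/15); ANCOVA with both terms, t(26)·SD·√(1 − rho²)·√(1.080 × 2/15). At SD 2 and rho 0.5: 2.048 × 2 × 1.000 × 0.365 = 1.50 against 2.056 × 2 × 0.866 × 0.379 = 1.35. At rho 0.7 the pair is 1.16 and 1.11; at rho 0.9 it is 0.67 and 0.68.

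The range of rho in which ANCOVA is below the MCID of 1.0 and the change contrast is above it depends on the SD: any rho below about 0.43 at SD 1.25; 0.52-0.60 at SD 1.5; 0.768-0.777 at SD 2; none at SD 2.5.

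**5. The other reading of changes.** If the outcome is the change within each walk, differenced between walks, its variance relative to the end-to-end change was 0.56-2.00 at rho 0.7 over 15 assumed combinations (end SD 2, pre-walk SD 1-2, correlation of the two pre-walk scores 0.7-0.9, pre/end correlation 0.4-0.6). The ratios in step 2 do not transfer to it.

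**The case against.** **The sentence may not be about A.3.** D.2 does not mention dose, and D.1 uses treatment both for the arms and for before versus after the spray. This stands: the ANCOVA point applies to the quoted sentence only if treatment means arm. On the other reading, A.3 has no analysis at all, and the same fix fills the gap.

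**Changes may mean within-walk change.** D.1 and D.2 both lend themselves to that reading, and step 2 does not cover it. A reader might infer that a within-walk change cannot be the A.3 quantity, because the Borg is scored from the start of each walk ("We will be measuring it every minute during the shuttle walk test starting from 0 minutes until the end of walk") and at Walk 2 that score follows dosing, so subtracting it would remove any effect on resting dyspnea. The documents do not support so firm a statement. Footnote 8 of Table 5 also schedules a Borg score 10 minutes before the walk, which is about dosing time. If that score precedes the spray, subtracting it removes no drug effect.

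**Distance is not simply a mediator.** The test is externally paced and Table 4 fixes the distance at each completed level, so running distance within a walk is largely the time axis. Patients also stop when too breathless, so one who is helped may walk further and stop at a similar score. Both points stand. Only total Walk 2 distance is clearly a post-dose outcome, and it should be shown beside the dyspnea estimate.

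**Little is at stake.** The summaries already promised would let a planner recover most SDs, D.2 does not exclude ANCOVA, and C.9 describes the test as reproducible, which points to a high rho and a small gain. This limits the weight of the point. It does not replace naming one analysis.

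**Conclusion.** The point holds as a minor one. D.2 leaves the only randomised contrast without a stated model, and its nearest wording, read as a contrast between arms, adjusts for neither Walk 1 dyspnea nor the stratum. Against an end-to-end change contrast with equal SDs, ANCOVA reduces variance by about 19-22% at rho 0.5 and 8-12% at rho 0.7, and makes no material difference at 0.9. When k·rho is near 1 it costs about 4%, or at most about 8% with an unbalanced, uninformative stratum. All of this rests on assumed rho, k and SD.

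Three stronger inferences are not supported. The change contrast is not biased or invalid; randomisation protects it, and coverage was nominal. No general claim can be made about whether the gain alters what the pilot can exclude at the MCID of 1.0, since that turns on an SD the documents do not give. The within-arm analysis and the 80%/0.778 statement are untouched. A.3 is secondary and declared unpowered.

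**What to change.** In D.2, state that A.3 is estimated by ANCOVA of end-of-Walk-2 Borg on arm, end-of-Walk-1 Borg and the resting-Borg stratum (0-3, 4-6). A repeated-measures model with a common Walk 1 mean plus the stratum would also serve. Report the adjusted high-minus-low difference with its 95% CI, the residual SD, the SD at each walk and the observed Walk 1/Walk 2 correlation.

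Do not adjust this estimate for total Walk 2 distance; report that alongside. Keep running distance or time in the separate minute-by-minute repeated-measures analysis.

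The cost is one or two sentences, no new data, two degrees of freedom and the small variance cost given above. One cost is interpretive: without distance in the model, similar end-of-walk scores must be read together with how far each arm walked.
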